#### **9.2. Recording of Adverse Events**

Safety will be assessed by monitoring and recording potential adverse effects using the Common Toxicity Criteria version 5.0 (CTCAE V5.0) at each study visit. Participants will be monitored by medical histories, physical examinations, and other studies. If CTCAE V5.0 grading does not exist for an adverse event, the severity of mild, moderate, severe, life-threatening, and death, corresponding to Grades 1-5, will be used whenever possible.

At each contact with the subject, the investigator will seek information on adverse events by non-directive questioning and, as appropriate, by examination. Adverse events may also be detected when they are volunteered by the subject during the screening process or between visits, or through physical examination, laboratory test, or other assessments. Information on all adverse events will be recorded in the source documentation. To the extent possible, adverse events will be recorded as a diagnosis and symptoms used to make the diagnosis recorded within the diagnosis event.

As much as possible, each adverse event or follow-up information will be evaluated to determine:

1. Severity grade (CTCAE V5.0 Grade 1-5)
2. Duration (start and end dates)
3. Relationship to the study treatment or process – [Reasonable possibility that AE is related: No (unrelated/ not suspected) or Yes (a suspected adverse reaction)]. If yes (suspected) - is the event possibly, probably or definitely related to the investigational treatment?
4. Action taken with respect to study or investigational treatment or process (none, dose adjusted, temporarily interrupted, permanently discontinued, unknown, not applicable)
5. Whether medication or therapy taken (no concomitant medication/non-drug therapy, concomitant medication/non-drug therapy)
6. Whether the event is serious

Once an adverse event is detected, it should be followed until its resolution or until it is judged to be permanent, and assessment should be made at each visit (or more frequently, if necessary) of

any changes in severity, the suspected relationship to the study treatment, the interventions required to treat it, and the outcome.

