#### **3.1.5. Post-PMT Administration Follow-Up**

Following a subject's final PMT administration or enrollment for those in the non-PMT arm, subjects enter the follow up phase. During this phase, the following will occur: (1) while remaining inpatient, daily maximum temperature, number of bowel movements, and any episodes of emesis will be recorded (based on electronic medical record) for 7 calendar days post-FMT or post-enrollment for the non-PMT arm; (2) in preparation for discharge from the hospital, subjects will record daily temperature, number of bowel movements, and any episodes of emesis for 7 days post last FMT/post-enrollment (subjects will be given a symptom diary card; a digital thermometer will also be provided); (3) subjects will be contacted by telephone or in-person for an interview focused on potential adverse events at 7 days (or next working day, not to exceed 10 days) after final FMT or after enrollment for non-PMT arm; (4) subjects will be contacted by telephone or in-person at 30 days (+/- 3 days) after final FMT or after enrollment for non-PMT arm for an interview focused on potential adverse events; (5) subjects will be contacted by telephone or in-person at 90 days (+/- 7 days) after final FMT or after enrollment for non-PMT arm for an interview focused on potential adverse events; (6) subjects will be contacted by telephone or in-person at 180 days (+/- 7 days) after final FMT or after enrollment for non-PMT arm for an interview focused on potential adverse events.

Telephone versus in-person follow-up will be determined based on subject preference. (If subjects prefer to be seen in person, but have been discharged from the hospital, a clinic visit with a study team member will be arranged). All FMT recipients (or their surrogates) will be given contact information for the study coordinator. As detailed above, subjects will be followed for 180 days following last investigational product administration or after enrollment for non-PMT arm. All subjects will be also provided a study contact telephone number on a copy of the

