#### 3.2.3. Primary Safety Endpoints

The primary safety endpoints will include:

- Frequency of solicited adverse events (AEs)
- Frequency of serious adverse events (SAEs)
- Frequency of AEs of special interest (AESIs)

See [Section 9](#) for additional details on adverse event definitions.

Monitoring post-PMT administration will occur in three phases:

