### **3.2.3.3. Post-PMT or Post-Enrollment Administration Follow-Up**

Safety endpoints assessed at the 7-day follow-up and all subsequent follow-ups will include fever, diarrhea, nausea, and vomiting. Safety endpoints assessed at the 30-day, 90-day, and 180-day follow-ups will include evidence of new metabolic disease, including hyperglycemia, thyroid disease, weight gain or loss.

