### **7.6. Other Evaluations, Measures**

Subjects will be provided with a diary and thermometer to keep track of their temperature (once a day), stool frequency, and any emesis. This diary will be reviewed with subjects at their 7-day follow-up visit.

For the exploratory aim, stool microbiome analysis will be performed on stool samples and peri-rectal swabs. Likewise, immune phenotypic analysis using flow cytometry may be performed on a subset of subjects using whole blood collected for clinical purposes, which would otherwise be discarded. Stool specimens will be obtained by placing flocced nylon swabs in available stool. Peri-rectal swabs will be obtained if possible. Blood will be collected from residual material available in EDTA ("purple top") vacutainer tubes already collected in the clinical laboratory.

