### **8.5.4. Safety Analysis**

All subjects entered into the study and randomized will have detailed information collected on adverse events starting at enrollment and for the duration of follow-up, as described elsewhere. The primary safety endpoints of frequency of AEs, SAEs, and AESIs will be described.

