### 9.1.3. Adverse Events of Special Interest (AESI)

Based on prior published experience with FMT-associated risks (Table 1), we have defined several adverse events of special interest.

In the initial, 60-minute bedside observation period following administration of investigational product, subjects will be monitored with close attention to the following:

- allergic reaction (temperature, skin rash, heart rate, or blood pressure change as already described) -- PMT-001, 002, and 003
- sepsis or shock (temperature, heart rate, or blood pressure change as already described) – PMT-001, 002, and 003
- bowel injury (abdominal pain change as already described) – PMT-001, 002, and 003
- aspiration (respiratory rate or oxygen saturation change as already described) – PMT-002 and 003 only

In the subsequent, 7-day monitoring period following administration of investigational product, subjects will be monitored with close attention to the following:

- donor-derived infection (temperature or abdominal pain change as already described) – PMT-001, 002, and 003
- worsening CDI (temperature, change in stool frequency/quantity or abdominal pain, or emesis as already described) – PMT-001, 002, and 003

In the subsequent, 30-, 90-, and 180-day monitoring periods, subjects will be monitored with close attention to the following:

- transmitted infection (temperature or abdominal pain change as already described) – PMT-001, 002, and 003
- recurrent CDI (temperature, change in stool frequency/quantity or abdominal pain, or emesis as already described) – PMT-001, 002, and 003
- metabolic changes (polydipsia, polyuria, weight gain, or weight loss) – PMT-001, 002, and 003

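### Solicited adverse events are a primary safety endpoint, but no solicited list is defined and the stated method is open questioning, so the count is at risk of being incomplete and unequal between arms

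*Combined protocol and SAP*

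**What the plan says.** Section 3.2.3 lists three primary safety endpoints, the first being "Frequency of solicited adverse events (AEs"), and sends the reader to Section 9 for definitions. Section 9 does not use the term solicited and gives no list, window or form for such events.

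On collection:

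- Section 9.2: at each contact "the investigator will seek information on adverse events by non-directive questioning and, as appropriate, by examination".
- Section 3.1.5: an interview is planned at 7 days ("for an interview focused on potential adverse events at 7 days"), and again at 30, 90 and 180 days. No question list is given.
- Section 3.1.5, on the diary: "subjects will record daily temperature, number of bowel movements, and any episodes of emesis for 7 days post last FMT/post-enrollment". The inpatient daily record in Sections 3.1.5 and 6.3.1 names the same three items, and Section 7.6 repeats the diary content.
- Table 3: a Symptom Review is marked at 30 and 60 minutes, in the first 3 days, and at 7, 30, 90 and 180 days. Its content is not described.

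On what is to be counted:

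- Section 3.2.3.3: "Safety endpoints assessed at the 7-day follow-up and all subsequent follow-ups will include fever, diarrhea, nausea, and vomiting".
- Section 9.1.3, for the 7-day period: "donor-derived infection (temperature or abdominal pain change as already described"). Abdominal pain also appears in the other 7-day event of special interest, and in two of the three listed for 30 to 180 days.
- Section 9.1.4: a relatedness threshold of at least a 50% increase in symptom severity, with hours of nausea per day as one measure.

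Section 8.5.4 on analysis: "The primary safety endpoints of frequency of AEs, SAEs, and AESIs will be described". Section 5.6 states that nobody is blinded.

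**The concern.** A solicited event is one that every subject is asked about by name, whether or not they would have raised it. Open questioning records what the subject chooses to mention. A protocol that names the first as its endpoint and the second as its method leaves the count undefined: two coordinators could follow the text, one prompting for nausea and one not, and report different frequencies.

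An unprompted symptom count depends on how readily subjects report and how often they are asked. In this trial subjects and staff know the assignment, and contact is more intensive after PMT than in the control arm. Safety is the sole secondary objective (Section 2.2), and the control arm helps to show which symptoms belong to the disease and which to the product. Symptoms that were not asked about at the time cannot be recovered reliably later.

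**Working it through.** The plan gives no expected adverse event rate and no power statement for safety, so there is no figure to reproduce. The check is mainly textual.

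**Step 1. Symptom signs used in the safety definitions, set against the stated records.**

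| Sign | Where it is used | Daily chart/diary item | Other stated collection |
|---|---|---|---|
| Fever | 3.2.3.1 to 3.2.3.3, 9.1.3 | Yes | Bedside vital signs |
| Diarrhea | 3.2.3.2, 3.2.3.3, 9.1.3 | Yes (bowel movements) | Chart review |
| Vomiting | 3.2.3.3, 9.1.3 | Yes (emesis) | Bedside observation |
| Nausea | 3.2.3.3, 9.1.4 | None stated | Named for follow-up contacts; no prompt given |
| Abdominal pain | 3.2.3.1, 9.1.3 | None stated | Bedside observation for 60 minutes, PMT recipients only |

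The Symptom Review applies to every row, but its content is not stated. The gap is widest for abdominal pain after the bedside hour, which is in neither the diary nor the Section 3.2.3.3 list.

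**Step 2. Can the definitions be applied?**

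- Section 9.1.3 relies on an abdominal pain change said to have been described already. Section 3.1.3 says only that subjects are watched for pain. Section 3.2.3.1 points to Section 3.2.1, which has no pain criterion.
- The Section 9.1.4 threshold compares with the 48 hours around the intervention. No described record captures hours of nausea before or after dosing.
- Examination does not fill the gap. Section 7.2 limits it to vital signs, and follow-up may be by telephone.

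**Step 3. Intensity of contact by arm (Sections 3.1.3, 3.1.4, 6.2.4).** PMT recipients have a 60-minute bedside check and 3 days of daily monitoring after each of up to three doses, so up to 3 × 3 = 9 monitored days. Controls have 3 days from enrollment.

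**Step 4. Mechanism, with assumed inputs only.** Observed rate = true rate × probability that an event is recorded. Enrollment is 60 PMT (30 + 30) and 30 control. Take a true rate of 30% in both arms:

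- Recorded 50% in both: 0.30 × 0.50 = 15% v 15%. Half the events are lost, with no false difference.
- Recorded 90% PMT, 60% control: 0.30 × 0.90 = 27% v 0.30 × 0.60 = 18%, a false +9 points (16.2 of 60 v 5.4 of 30 subjects).
- Recorded 60% PMT, 90% control: 18% v 27%, a false −9 points.

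With the same 30-point gap in recording, a true rate of 10% gives 0.10 × 0.30 = 3 points and a true rate of 50% gives 0.50 × 0.30 = 15 points, in either direction. The documents support none of these rates. The example shows only that the sign depends on which arm is better ascertained.

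**The case against.** The strongest reply is that open questioning is one channel among several. Table 3 separates the Symptom Review from the Adverse Event Check and schedules it at every follow-up. Section 3.2.3.3 names four symptoms as assessed from day 7 onward. Section 9.1.3 asks for close attention to abdominal pain up to 180 days. Bedside observation covers pain and vomiting. Section 6.3.1 speaks of tracking symptoms in general, and Section 7.1 adds record review. The case report forms and the diary card are not in the documents and may carry prompts. Laboratory and chart endpoints in Section 3.2.3.2 and the outcomes in Section 7.9.2, such as mortality and bacteremia, do not depend on what a subject volunteers.

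Much of this stands, and it rules out several stronger readings:

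- A reader might infer that the endpoint is under-counted as a matter of fact. The documents give no rates, so this is a risk and is not shown.
- A reader might infer a false excess in the PMT arms of some given size. Neither sign nor size can be derived.
- A reader might infer that nausea and abdominal pain have no prospective record at all. The supportable statement is that neither has a stated daily item.
- A reader might infer from Section 8.5.4 that solicited and unsolicited events will be pooled. The sentence may simply be shorthand for the list in Section 3.2.3. It does not say either way.
- A reader might infer that a formal comparison is compromised. The analysis is descriptive, so no test or error rate is affected.

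What the reply does not answer is the mismatch itself. A table row without content and a list of names are not a method, and the only questioning method stated is open.

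**Conclusion.** The point holds as a gap in definition and method. Solicited adverse events are a primary safety endpoint with no list and a stated questioning method that does not fit. Nausea and abdominal pain have no stated daily item, and abdominal pain has no stated collection method after the bedside hour. The endpoint is at risk of under-counting and of unequal ascertainment in an open-label trial. Size and direction cannot be derived, and no figure in the plan changes. The conclusion assumes that the forms outside the documents do not already carry a fixed prompt. If they do, the remedy reduces to stating this in the protocol and aligning the wording. It is a worthwhile, inexpensive correction, and it does not affect the primary efficacy analysis.

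**What to change.** 1. In Section 9.2, define the solicited events from Sections 3.2.3.2, 3.2.3.3 and 9.1.3. Collect the symptom items with the same fixed yes/no checklist at every scheduled Symptom Review in all arms, and state this as the content of that row in Table 3. Keep open questioning for unsolicited events. The 30- and 60-minute reviews have no counterpart in controls, so tabulate bedside events apart.
2. Add nausea (including hours per day) and abdominal pain to the diary and the inpatient daily record, with an *unable to report* entry where the subject cannot self-report.
3. In Section 8.5.4, describe solicited and unsolicited adverse events separately by arm.

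The cost is about one case report form page, two diary items and revised wording; no treatment changes. There are three downsides. More mild events will be counted. Some self-reports will be missing in the sickest subjects, such as those on vasopressors or enrolled through a decision-maker. A checklist also reduces open-label reporting bias without removing it, and it does not equalize the number of monitored days, so the observation time in each arm should be shown beside the frequencies.

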### **9.3. Reporting of Adverse Events and Unanticipated Problems**

#### **Reporting period**

Adverse events will be reported from the time of informed consent until study completion.

#### **Investigator reporting: notifying the study sponsor**

The sponsor must be notified within 24 hours of learning of an SAE occurrence, regardless of suspected causality (e.g., relationship to study drug(s) or study procedure or disease progression).

At the time of the initial notification, the following information should be provided:

- Study identifier
- Subject number
- A description of the event
- Date of onset
- Current status
- Whether study treatment was discontinued
- The reason the event is classified as serious
- Investigator assessment of the association between the event and study treatment

Follow-up information on SAEs should be reported when updates are available, as a follow-up to the initial SAE report, and should include both the follow-up number and report date. New information on ongoing serious adverse events should be provided promptly to the sponsor. The follow-up information should describe whether the event has resolved or continues, if there are any changes in assessment, if and how it was treated, and whether the patient continued or withdrew from study participation. The investigator must follow the event to resolution or until the event is deemed and documented irreversible, whichever is longer.

Recurrent episodes, complications, or progression of the initial SAE must be reported as the follow-up to the original episode within 24 hours of the investigator receiving the follow-up information. An SAE considered completely unrelated to a previously reported one should be reported separately as a new event.

In addition, all unexpected fatal or life-threatening suspected adverse reactions will be reported to the FDA as soon as possible but in no case later than 7 calendar days after the sponsor's initial receipt of the information. Other SAEs that are both, unexpected and related to the study drugs (SUSAR) will be reported to the FDA as soon as possible but no later than 15 calendar days after knowledge of the event.

#### **Investigator Reporting: Local Reporting Requirements**

The investigator will report AEs and SAEs to his/her IRB/EC of record and other local regulatory groups per the local requirements.

### **9.3.1. Pregnancy**

Pregnancy, in and of itself, is not regarded as an AE unless there is suspicion that study drug or process may have interfered with the effectiveness of a contraceptive medication or method. When a pregnancy has been confirmed in a subject during maternal or paternal exposure to study drug and/or process, the following procedures should be followed to ensure subject safety:

Data on fetal outcome will be collected for regulatory reporting and drug safety evaluation. Follow-up should be conducted for each pregnancy to determine outcome, including spontaneous or voluntary termination, details of the birth, and the presence or absence of any birth defects, congenital abnormalities, or maternal and/or newborn complications. A case report form will capture these outcomes for pregnant subjects, and the sponsor will be notified within 24 hours of recorded an adverse event related to pregnancy.

### **9.4. Toxicity Management, Stopping Rules and Study Termination**

Enrollment and administration of the study product will be halted pending review by the study staff and Data Safety Monitoring Board (DSMB) if any subject experiences an AE that is assessed as (1) serious (i.e., that results in significant symptoms preventing normal daily activities or requiring hospitalization), (2) unexpected, and (3) related to administration of the study product. Enrollment and administration of the study product will be halted pending review by the study staff and Data Safety Monitoring Board (DSMB) if any subject experiences a suspected or proven infection assessed as related to the study product. The review of these adverse events, and any decision to prematurely stop subject enrollment, will be determined by the Medical Director and DSMB.

### **9.5. Medical Monitoring**

It is the responsibility of the Principal Investigator to oversee the safety of the study at his/her site. This safety monitoring will include careful assessment and appropriate reporting of adverse events as noted above.

#### **9.5.1. Data and Safety Monitoring Plan**

A Drug Safety Monitoring Plan has been developed based on risk and is described in a separate document. The monitoring plan will include the following components:

- Principal Investigator monitoring
- The Sponsor Medical Director
- Data Safety and Monitoring Board (DSMB)

#### **9.5.2. Data Safety Monitoring Board**

An independent DSMB will perform evaluations of safety data at specified intervals throughout the study and make recommendations to the Sponsor regarding further conduct of the study. The DSMB will evaluate subject safety as specified in the DSMB Charter.

## **10. Study Administration, Data Handling and Record Keeping**

### ***10.1. Confidentiality***

Information about study subjects will be kept confidential and managed according to the requirements of the Health Insurance Portability and Accountability Act of 1996 (HIPAA).

Those regulations require a signed subject authorization informing the subject of the following:

- What protected health information (PHI) will be collected from subjects in this study
- Who will have access to that information and why
- Who will use or disclose that information
- The rights of a research subject to revoke their authorization for use of their PHI.

In the event that a subject revokes authorization to collect or use PHI, the investigator, by regulation, retains the ability to use all information collected prior to the revocation of subject authorization. For subjects that have revoked authorization to collect or use PHI, attempts should be made to obtain permission to collect at least vital status (i.e. that the subject is alive) at the end of their scheduled study period.

### ***10.2. Future Use of Stored Specimens and Data***

Stool and blood specimens collected as above ([Section 7.6](#)) may be preserved in frozen storage for future analyses. The data generated from those specimens will only be used for research purposes. It will not be shared with subjects or be used to direct treatment.

### ***10.3. Data Collection and Management***

Case Report Forms (CRFs) will be completed, with copies either printed and stored in binders in a secure location or securely stored in an approved electronic system to which only study personnel will have access. Subject diaries will also be collected and stored in a secure location. Subjects will be assigned a unique study identification number, and PHI will be kept separately with a master file stored on a secure, password-protected computer. Linkage to PHI will be stored until study analysis and publication completion, and then will be destroyed.

Exploratory microbiome analysis will be performed on stool specimens and exploratory immune response phenotyping using flow cytometry will be performed using a unique study identification number, with no associated PHI. The exploratory analysis of subject microbiome composition (will or will not) be shared with the subjects treating physician.

Stool and blood specimens will be coded to maintain patient confidentiality and will be stored according to regulations. The subject specific stool samples be tracked with a master file linking PHI to study ID numbers, which will be kept on a secure, password-protected computer.

